# 11.5. Sample Size Determination

The Dose Escalation Part of this study consists of mCRM with EWOC design with at least 3 DLT-evaluable subjects per dose level. Sample size has been determined by practical considerations and no formal statistical assessment has been performed for the Dose Escalation Part.

A total of approximately 12 subjects will be enrolled between Dose Escalation and Dose Finding for each of the Q3W Dosing Cohorts evaluated in Dose Finding. For the alternative dosing cohorts evaluated in Dose Finding, a total of approximately 12 subjects will be enrolled into each cohort. RDE(s) will be determined based on the risk and benefit assessment.

For the Dose Expansion Part, there are 4 planned expansion cohorts (HER3-high, HR-positive [6.4 mg/kg], HER3-high, HR-positive [4.8 mg/kg], HER3-low, HR-positive [6.4 mg/kg] and HER3-high, TNBC [6.4 mg/kg]):

• Approximately 60 eligible subjects with HER3-high, HER2-negative, HR-positive disease will be randomized into 1 of 2 cohorts: 4.8 mg/kg or 6.4 mg/kg.

- Subjects with HER3-low, HER2-negative, HR-positive breast cancer will not be randomized. Approximately 20 eligible subjects in this setting will be enrolled into a HER3-low, HR-positive (6.4 mg/kg) cohort.
- Subjects with HER3-high, TNBC will not be randomized. Approximately 30 eligible subjects in this setting will be enrolled into an HER3-high, TNBC (6.4 mg/kg) cohort.

A total of approximately 110 subjects will be enrolled into the Dose Expansion Part.

In HER3-high, HR-positive cohorts of the Dose Expansion Part, if target ORR is more than 10% (null hypothesis: ORR  $\le$ 0.10, alternative hypothesis: ORR  $\ge$ 0.10), then the probability of no response out of 30 subjects will be less than 5%. The probability that more than 6 responders out of 30 subjects (ORR  $\ge$ 20%) are observed will be less than 5% under the null hypothesis with ORR  $\le$ 0.10 but more than 80% under alternative hypothesis with ORR = 0.30.

In the HER3-low, HR-positive cohort of the Dose Expansion Part, if target ORR is more than 10% (null hypothesis: ORR  $\le$ 0.10, alternative hypothesis: ORR  $\ge$ 0.10), then the probability of no response out of 20 subjects will be less than 15%. The probability that more than 3 responders out of 20 subjects (ORR  $\ge$ 15.0%) are observed will be less than 15% under the null hypothesis with ORR  $\le$ 0.10 but more than 75% under alternative hypothesis with ORR = 0.25.

In the HER3-high, TNBC cohort of the Dose Expansion Part, if target ORR is more than 20% (null hypothesis: ORR  $\le$ 0.20, alternative hypothesis: ORR  $\ge$ 0.20), then the probability of no response out of 30 subjects will be less than 5%. The probability that more than 9 responders out of 30 subjects (ORR  $\ge$ 30.0%) are observed will be less than 10% under the null hypothesis with ORR  $\le$ 0.20 but more than 80% under alternative hypothesis with ORR = 0.40.

The probability values for the sample size are derived based on binomial distribution using SAS® version 9.4.

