The data cutoff for the primary analysis will occur after all subjects have either discontinued from the study or have been followed for at least 9 months following the first dose of study treatment, whichever is earlier. The primary analysis data cutoff may be extended if emerging data show responses are occurring later. The final analysis of the study will occur after all subjects have discontinued the study. Data collected beyond the primary analysis cut-off time point will be presented as appropriate in a Clinical Study Report addendum. Data analyses will also be conducted during the Dose Escalation and Dose Finding Parts.

Descriptive statistics will be provided for selected demographic, safety, and PK data by cohort and time as appropriate. Descriptive statistics on continuous data will include means, medians, standard deviations, and ranges (as well as geometric means and geometric coefficient of variation for Cmax and AUC PK parameters), while categorical data will be summarized using frequency counts and percentages. Graphical summaries of the data may be presented. Efficacy Analyses:

Efficacy variables will include ORR, DCR, DOR, CBR, TTR, PFS, using RECIST version 1.1 and OS.

The efficacy variables will be listed and summarized. For ORR and DCR, point estimates and 2-sided 95% exact binomial confidence intervals will be provided. Time to event variables including DOR, TTR, PFS, and OS will be summarized descriptively using the Kaplan-Meier method. PFS is defined as the time from the date of the first dose to the earlier of the dates of the first objective documentation of radiographic PD or death due to any cause. Censoring rules for the time-to-event endpoints such as PFS and OS analysis will be specified in the statistical analysis plan (SAP). Descriptive statistics for the best percent change in the sum of diameters of measurable tumors will be provided. A waterfall plot of the best percent change from screening in the sum of diameters for each subject will be presented.

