#### 11. STATISTICAL METHODS

#### 11.1. General Statistical Considerations

The primary analysis is to assess the efficacy, safety, and tolerability of U3-1402 in subjects with HER3-positive metastatic breast cancer and to determine the MTD/RDE or establish the safety and tolerability of the maximum administered dose of U3-1402.

The data cutoff for the primary analysis will occur after all subjects have either discontinued the study or have been followed for at least 9 months following the first dose of study treatment, whichever is earlier. The primary analysis data cutoff may be extended if emerging data show responses are occurring later. The final analysis of the study will occur after all subjects have discontinued from the study. Data collected beyond the primary analysis cut-off time point will be presented as appropriate in a Clinical Study Report (CSR) addendum.

The data analyses will also be conducted during the Dose Escalation and Dose Finding Parts.

Descriptive statistics will be provided for selected demographic, safety, and PK data by cohort and time as appropriate. Descriptive statistics on continuous data will include means, medians, standard deviations, and ranges (as well as geometric means and geometric coefficient of variation for Cmax and AUC PK parameters), while categorical data will be summarized using frequency counts and percentages. Graphical summaries of the data may be presented.

Assessments of change from baseline to post-treatment or the ratio of post-treatment to baseline will include only those subjects with both baseline and post-treatment measurements. The last nonmissing value of a variable taken before the first dose of study drug will be used as the baseline value, unless otherwise specified. In general, missing or dropout data will not be imputed for the purpose of data analysis, unless otherwise specified.

Safety analyses will be performed based on the safety analysis set. Analysis of PK parameters will be based on the PK analysis set and biomarker analyses will be based on the Full Analysis Set (FAS). Efficacy endpoints will be analyzed based on the FAS. Data will be summarized by cohort, RDE cohort(s) (Dose Escalation and Dose Finding Parts), and overall.

A detailed Statistical Analysis Plan (SAP) describing the methodology to be used in the final analysis will be prepared and finalized before database lock. Statistical methods described within this document may be changed based on advances in research.

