## 11.4. Statistical Analysis

## 11.4.1. Efficacy Analyses

Efficacy endpoints will include ORR (the sum of CR and PR rates); DCR (the sum of CR rate, PR rate, and SD rate), DOR, CBR, TTR, PFS, OS, and percent change in target lesion(s). Tumor responses will be assessed by an Investigator and an independent central imaging CRO according to RECIST 1.1.

The efficacy endpoints will be listed and summarized. For ORR and DCR and CBR, point estimates 2-sided 95% exact binomial confidence intervals will be provided. Time to event variables including PFS, OS, TTR, and DOR will be summarized descriptively using the Kaplan-Meier method. PFS is defined as the time from the date of the first dose to the earlier of the dates of the first objective documentation of radiographic PD or death due to any cause. Censoring rules for the PFS analysis will be specified in the SAP.

Descriptive statistics for the best percent change from baseline in the sum of diameters of measurable tumors will be provided. A waterfall plot of the best percent change in the sum of diameters for each subject will be presented.

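### Do the response probabilities in Section 11.5 overstate what the planned 95% confidence interval can show?

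*Combined protocol and SAP*

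**What the plan says.** Section 11.5 covers three expansion settings and is repeated in the synopsis. Each has a null ORR, an alternative ORR and a responder count.

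- **HER3-high, HR-positive (30 per dose cohort):** null 10%. More than 6 responders has probability below 5% at the null, "but more than 80% under alternative hypothesis with ORR = 0.30".
- **HER3-low, HR-positive (20):** null 10%. "The probability that more than 3 responders out of 20 subjects" are seen is put below 15% at the null, "but more than 75% under alternative hypothesis with ORR = 0.25".
- **HER3-high TNBC (30):** null 20%. "The probability that more than 9 responders out of 30 subjects" are seen is put below 10% at the null, "but more than 80% under alternative hypothesis with ORR = 0.40".

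The analysis itself is in Section 11.4.1: "For ORR and DCR and CBR, point estimates 2-sided 95% exact binomial confidence intervals will be provided". The statistical part of the synopsis says the same for ORR: "For ORR and DCR, point estimates and 2-sided 95% exact binomial confidence intervals will be provided". Section 11.1 includes efficacy in the primary analysis: "The primary analysis is to assess the efficacy, safety, and tolerability of U3-1402". Neither Section 11.4.1 nor the synopsis names a test, uses a 5%, 15% or 10% level, or says what is done with the counts. Section 11.6 leaves further methods to the SAP, whose text is not in the supplied document.

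**The concern.** Stated hypotheses, a bound at the null and a high probability at the alternative look like a test with its power. A reader then goes to Section 11.4.1 to find the test and finds a 95% interval. If that interval is taken as the test, the design seems to lose much of its power, most of all in HER3-low, where a figure above 75% becomes 38%.

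The two readings can also conflict on the same data. With 5 responders of 20, the count in Section 11.5 is exceeded, yet the 95% interval still contains 10%. One report could say the criterion was met and another that a 10% rate was not excluded. At stake is how the Section 11.5 hypotheses may be described in the study report.

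**Working it through.** **Inputs.** From Section 11.5: n = 30, 20, 30; counts of at least 7, 4 and 10 (more than 6, 3 and 9); null p0 = 0.10, 0.10, 0.20; alternative p1 = 0.30, 0.25, 0.40. From Section 11.4.1: two-sided 95% exact interval. The 30 per HER3-high HR-positive cohort assumes that the roughly 60 subjects split equally, which fits the denominator of 30 in Section 11.5.

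**Step 1: reproduce Section 11.5.** P(X ≥ r) = Σ C(n,k) p^k (1−p)^(n−k), summed over k = r to n.

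| Setting | Count | At p0 | Stated | At p1 | Stated |
|---|---|---|---|---|---|
| HER3-high HR-positive | ≥7/30 | 2.6% | <5% | 84.0% | >80% |
| HER3-low | ≥4/20 | 13.3% | <15% | 77.5% | >75% |
| TNBC | ≥10/30 | 6.1% | <10% | 82.4% | >80% |

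All six agree. The no-response probabilities in the same section also hold: 0.9^30 = 4.2% (<5%), 0.9^20 = 12.2% (<15%), 0.8^30 = 0.12% (<5%). One responder fewer gives 7.3%, 32.3% and 12.9% at the null, so these are the smallest counts that respect the stated bounds.

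**Step 2: the 95% interval read against the null.** The exact (Clopper-Pearson) lower limit at x responders is the 2.5% quantile of Beta(x, n−x+1). Find the smallest x whose lower limit exceeds p0, then apply the formula of Step 1.

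| Setting | One count short: lower limit | First count that excludes p0: lower limit | At p0 | At p1 |
|---|---|---|---|---|
| HER3-high HR-positive | 7/30: 9.9% | 8/30: 12.3% | 0.8% | 71.9% |
| HER3-low | 5/20: 8.7% | 6/20: 11.9% | 1.1% | 38.3% |
| TNBC | 11/30: 19.9% | 12/30: 22.7% | 0.9% | 56.9% |

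**Step 3: where the readings part.** These are results that exceed the Section 11.5 count while the interval still contains the null. Their probability at the alternative is the difference between Steps 1 and 2.

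- HER3-high HR-positive, 7/30: 84.05% − 71.86% = 12.2%.
- HER3-low, 4/20 or 5/20: 77.48% − 38.28% = 39.2%.
- TNBC, 10/30 or 11/30: 82.37% − 56.89% = 25.5%.

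**Step 4: why the probabilities differ.** The interval criterion has a null probability of about 1% in every setting, whereas the counts allow 2.6%, 13.3% and 6.1%. A stricter threshold must be reached less often at the same n and p1. Exact two-sided intervals at 90%, 70% and 80% have lower limits of 11.5% at 7/30, 10.5% at 4/20 and 21.8% at 10/30. They first exclude the null at exactly the Section 11.5 counts and give back 84.0%, 77.5% and 82.4%. So the gap comes entirely from the change of level.

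**Step 5: can the counts be read from the planned output?** 6/30 = 20%, 3/20 = 15% and 9/30 = 30%, so exceeding a count is the same as an observed ORR above 20%, 15% or 30%. Section 11.4.1 reports the observed ORR.

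**The case for a change.** The strongest case for a change is that hypotheses invite an answer, and the protocol does not say how they will be answered. Efficacy is part of the primary objective of Dose Expansion, the study is open-label, and the SAP need only be final before database lock. Someone could therefore choose between the count and the interval after seeing responses. In HER3-low, at the ORR the protocol itself chose, that choice matters in about two trials of five. That cohort also has no slack: with more than 3 responders kept as the criterion, 19 subjects give 73.7% at the alternative and 21 give 15.2% at the null, while enrolment is only approximately 20.

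What stands is that the link is unwritten and the two readings can disagree. The rest weighs less. The estimate and the 95% interval are fixed in advance and would be reported whichever reading is favoured, so a reader of 5/20 sees both the 25% and the interval of 8.7% to 49.1%. The drift at 19 or 21 subjects concerns a planning figure for approximate enrolment and has no bearing on the interval, which is computed at the actual n. An added sentence would also be hard to word safely. To say that no test is planned goes beyond what the protocol shows, since methods are left to the SAP. To print 72%, 38% and 57% beside the design would bring in the very test that such a sentence denies.

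**Conclusion.** No change follows. Section 11.5 contains no arithmetic error and no power shortfall: each probability is correct, at exactly 30, 20 and 30 subjects, for the event it describes. The 71.9%, 38.3% and 56.9% are also correct, but only if the descriptive interval of Section 11.4.1 is turned into a test of the null, which no section does.

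What is left is a gap that analysts fill sensibly: treat the counts as planning figures and report responders, estimate and interval together. If the SAP specifies a test, it settles the matter. A clarifying sentence would alter no result, sample size or decision, because the interval is valid and no go/no-go rule uses the counts. The conclusion rests on equal allocation in the HER3-high HR-positive cohorts and on the protocol text alone, without the SAP.

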## 11.6. Statistical Analysis Process

The clinical study will be analyzed by DS or its agent/CRO followed by this protocol, and SAP which will demonstrate all methodologies and displays/shells for statistical analyses.

The SAP will provide the statistical methods and definitions for the analysis of the efficacy and safety data, as well as describe the approaches to be taken for summarizing other clinical study information such as subject disposition, demographic and baseline characteristics, study drug exposure, and prior and concomitant medications. The SAP will also include a description of how missing, unused, and spurious data will be addressed.

To preserve the integrity of the statistical analysis and clinical study conclusions, the SAP will be finalized prior to database lock.

All statistical analyses will be performed using SAS® Version 9.3 or higher (SAS Institute, Cary, NC 27513).

# 11.7. Specification of Modified Continuous Reassessment Method with Escalation with Overdose Control

# 11.7.1. Bayesian Logistic Regression Model for Modified Continuous Reassessment Method

The dose-toxicity relationship for mCRM with EWOC principle will be described by following 2-parameter BLRM:

 $logit(\pi(d)) = log(\alpha) + \beta log(d/d^*), \alpha > 0, \beta > 0$ 

where  $logit(\pi(d)) = ln(\pi(d)/(1-\pi(d)))$ ,  $\pi(d)$  is the probability of a DLT or the DLT rate at dose d. Doses are rescaled as  $d/d^*$  with the reference dose  $d^* = 9.7$  mg/kg. As a consequence,  $log(\alpha)$  is equal to  $logit(\pi(d^*))$  at dose  $d^*$ . Note that for a dose equal to zero, the probability of toxicity is zero.

## 11.7.2. Prior Specification for Bayesian Logistic Regression Model Parameters

The Bayesian approach requires the specification of a prior distribution for the BLRM parameters. A minimally-informative bivariate normal prior for the model parameters  $(\log(\alpha), \log(\beta))$  is obtained as follows:

- Based on extrapolation of nonclinical toxicology studies in monkeys, the MTD is projected to be greater than 9.7 mg/kg in humans (the HNSTD of monkeys is 30 mg/kg and assuming humans and monkeys are equally sensitive, the MTD is projected to be greater than 9.7 mg/kg in humans). The median prior probabilities of DLT are set to be approximately 8.0% and 24.5% at 1.6 mg/kg (projected starting dose for dose escalation using mCRM) and at 9.7 mg/kg, respectively.
- For the remaining doses, the medians of probability of DLT are assumed linear in log-dose on the logit-scale.
- Based on the above medians for the probability of DLT at each dose and wide prior credible intervals (obtained from minimally informative Beta distributions), the optimal parameters of the bivariate normal distribution can be obtained as follows:

Parameters	Means	Standard deviations	Correlation
$log(\alpha), log(\beta)$	(-1.0981, -0.4913)	(2.0445, 0.8677)	-0.3317

## 11.7.3. Escalation with Overdose Control Principle

Dose recommendation for the next cohort will be based on summaries of the posterior probability of the DLT rate for provisional doses: 1.6, 3.2, 4.8, 6.4, and 8.0 mg/kg. After subjects of each cohort complete DLT evaluation during Cycle 1, the posterior distributions of the DLT rate are derived for all provisional dose levels based on the BLRM using the DLT outcome data from all assessed doses and a pre-specified prior distribution for the model parameters. The posterior probability of the DLT rate in the following 4 intervals at each dose level will then be calculated:  $0\% \leq DLT$  rate  $\leq 16\%$  as the DLT rate interval for under-dosing, 16% < DLT rate  $\leq 33\%$  as the target DLT rate interval, 33% < DLT rate  $\leq 60\%$  as the DLT rate interval for excessive toxicity, and 60% < DLT rate  $\leq 100\%$  as the DLT rate interval for

unacceptable toxicity, and used for dose recommendation for the next cohort according to the EWOC principle. The above provisional doses are based on an initial estimate of the human MTD of 9.7 mg/kg using the HNSTD of monkeys in nonclinical toxicology studies (30 mg/kg). It is therefore conceivable that the posterior probability of DLT rate for dose recommendation may be generated using alternative provisional doses as long as the predicted exposure increments are no more than 100% (Section 3.1.3).

The EWOC principle requires that the mCRM recommended dose for the next cohort of subjects is the one with the highest posterior probability of the DLT rate in the target DLT rate interval of 16% < DLT rate  $\le 33\%$  among all doses fulfilling the overdose control constraint: there is less than 25% of probability for the DLT rate  $\ge 33\%$  (probability for excessive or unacceptable toxicity).

## 12. DATA INTEGRITY AND QUALITY ASSURANCE

The Investigator/investigational site will permit study-related monitoring, audits, IRB/IEC review and regulatory inspections by providing direct access to source data/documents. Direct access includes permission to examine, analyze, verify, and reproduce any records and reports that are important to the evaluation of a clinical study.

## 12.1. Monitoring and Inspections

The CRO monitor and regulatory authority inspectors are responsible for contacting and visiting the Investigator for the purpose of inspecting the facilities and, upon request, inspecting the various records of the study (eg, CRFs, source data, and other pertinent documents).

The verification of adherence to the protocol; completeness, accuracy, and consistency of the data; and adherence to ICH Good Clinical Practice (GCP) and local regulations on the conduct of clinical research will be accomplished through a combination of onsite visits by the monitor and review of study data remotely. The frequency of the monitoring visit will vary based on the activity at each site. The monitor is responsible for inspecting the CRFs and ensuring completeness of the study essential documents. The monitor should have access to subject medical records and other study-related records needed to verify the entries on the CRFs. Detailed information is provided in the monitoring plan.

The monitor will communicate deviations from the protocol, SOPs, GCP, and applicable regulations to the Investigator and will ensure that appropriate action (s) designed to prevent recurrence of the detected deviations is taken and documented.

The Investigator agrees to cooperate with the monitor to ensure that any problems detected in the course of these monitoring visits are addressed to the satisfaction of the Sponsor and documented.

In accordance with ICH GCP and the Sponsor's audit plans, this study site may be selected for audit by representatives from the Sponsor. Audit of site facilities (eg, pharmacy, drug storage areas, laboratories) and review of study related records will occur in order to evaluate the study conduct and compliance with the protocol, ICH GCP, and applicable regulatory requirements. The Investigator should respond to audit findings. In the event that a regulatory authority informs the Investigator that it intends to conduct an inspection, the Sponsor shall be notified immediately.

#### 12.2. Data Collection

The Investigator or study staff will enter the data in the eCRF (see Section 17.6) in accordance with the CRF Completion Guidelines that are provided by the Sponsor.

eCRF completion should be kept current to enable the monitor to review the subject's status throughout the course of the study. The eCRF will be completed, reviewed and signed off or e-signed by the Investigator after all queries have been satisfactorily resolved.

The Investigator e-signs according to the study data flow.

Any data recorded on the study CRF will be collected and included in the database according to Clinical Data Interchange Standards Consortium (CDISC) standards and subjected to the same procedures as other data.

## 12.3. Data Management

Each subject will be identified in the database by a unique Subject Number as defined by the Sponsor.

To ensure the quality of clinical data across all subjects and study sites, a Clinical Data Management review will be performed on subject data according to specifications given to Sponsor or CRO. Data will be vetted both electronically and manually for CRFs and the data will be electronically vetted by programmed data rules within the application. Queries generated by rules and raised by reviewers will be generated within the Electronic Data Capture (EDC) application. During this review, subject data will be checked for consistency, completeness, and any apparent discrepancies. To resolve any questions arising from the Clinical Data Management review process for eCRFs queries will be raised and resolved within the EDC application.

Data received from external sources such as central laboratories will be reconciled to the clinical database.

SAEs in the clinical database will be reconciled with the safety database.

All medical and surgical history and Adverse Events will be coded using Medical Dictionary for Regulatory Activities (MedDRA). All prior cancer therapy and prior/concomitant medications entered into the database will be coded by using the latest version of World Health Organization Drug Dictionary.

